## 5.4.1. Dose Modifications for Patients with Renal Impairment

Patients ≥17 years of age who develop an elevated creatinine while on study should have their creatinine clearance (CrCl) recalculated and dose of valganciclovir adjusted per Table 4.

An estimated CrCl in adults is calculated from serum creatinine by the following formulas:

For serum creatinine measured in mg/dL:

For males = 
$$(140 - age [years]) \times (body weight [kg]) = XX mL/min$$
  
(72) × (serum creatinine [mg/dL])

For females = 
$$(140 - age [years]) \times (body weight [kg]) = XX mL/min \times 0.85$$
  
(72) × (serum creatinine [mg/dL])

For serum creatinine measured in µmol/L:

For males = 
$$(140 - age [years]) \times (body weight [kg]) \times 1.23 = XX mL/min$$
  
Serum creatinine (µmol/L)

For females = 
$$(140 - age [years]) \times (body weight [kg]) \times 1.23 = XX \text{ mL/min} \times 0.85$$
  
Serum creatinine (µmol/L)

For patients already receiving a dose of valganciclovir lower than that recommended in Table 4, the Investigator should discuss the amount of dose reduction with the Medical Monitor.

Table 4: Valganciclovir Dosing for Patients with Renal Impairment

Creatinine Clearance (mL/minute)	Valganciclovir Dose
≥60	900 mg once daily
40–59	450 mg once daily
25–39	450 mg every 2 days
10–24	450 mg twice weekly
<10 (on hemodialysis)	Not recommended (discuss with Medical Monitor)

Source: Valcyte USPI 2021(Genentech 2021) and SmPC 2018 (Roche 2018)

Note: Patients  $\geq$ 17 years of age receiving hemodialysis (CrCl less than 10 mL/min) cannot use valganciclovir tablets because the daily dose of valganciclovir tablets required for these patients is less than 450 mg. In this case the Investigator will have the option of administering ganciclovir IV at 5 mg/kg QD, after discussion with the Study Medical Monitor.

Patients 12 to 16 years of age who develop an elevated creatinine while on study should have their CrCl recalculated (by a modified Schwartz formula per Section 5.2.2) and dose of valganciclovir adjusted based on body surface area (BSA).

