# 5.2.2. Valganciclovir Administration

The daily dose of valganciclovir for patients ≥17 years of age is 900 mg orally (continuous treatment) in combination with nanatinostat. Patients with a CrCl 50-59 mL/min at study entry will receive valganciclovir 450 mg orally once daily as per Table 4. Patients will continue to receive nanatinostat plus valganciclovir in 28-day cycles until discontinuation as described in Section 7.2.3.

The daily dose of valganciclovir for patients ≤16 years of age is based on body surface area (BSA) and CrCl derived from a modified Schwartz formula, and is calculated using the equation below:

Adolescent dose (mg) =  $7 \times BSA \times Schwartz$  Creatinine Clearance

$$Mosteller\ BSA\ (m^2) = \sqrt{\frac{Height\ (cm)\ x\ Weight\ (kg)}{3600}}$$
 
$$Schwartz\ Creatinine\ Clearance\ (mL\ /\ min\ /\ 1.73m^2)\ = \frac{k\ x\ Height\ (cm)}{Serum\ Creatinine\ (mg\ /dL)}$$

Note: k value is 0.55 (boys <13 years and girls <16 years) or 0.7 (boys aged 13 to 16 years).

Patients should be monitored for serum creatinine levels regularly, consider changes in height and body weight, and adapt the valganciclovir dose as appropriate. Valganciclovir tablet dose is

determined based on the calculated valganciclovir dose in mg and available tablet strength (450 mg)  $\pm 10\%$  range of the tablet strength. For example, if the calculated dose exceeds 900 mg, a maximum dose of 900 mg should be administered. If the calculated dose is between 900 mg and 810 mg, a 900 mg dose (two 450 mg tablets) should be taken. If the calculated dose is between 809 mg and 405 mg, 450 mg dose (one 450 mg tablet) should be taken.

Adequate hydration should be maintained for all patients. For patients who develop an elevated creatinine while on study, their dose of valganciclovir should be adjusted (see Section 5.4.1).

In patients who are unable to tolerate oral dosing of valganciclovir, the Investigator will have the option of administering ganciclovir intravenously (IV) at 5 mg/kg QD. In patients who are receiving a dose of valganciclovir less than 900 mg orally once daily, the dose of ganciclovir will be reduced accordingly using the ratio of 900 mg valganciclovir to 5 mg/kg ganciclovir.

Valganciclovir absorption is affected by food. Therefore, patients should be instructed to take both valganciclovir and nanatinostat with food and not fasting.

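### The Table 4 note offers dialysis patients IV ganciclovir at 5 mg/kg QD, the dose Section 5.2.2 pairs with full-dose valganciclovir, while saying they need less than 450 mg a day

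*Protocol*

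**What the plan says.** Table 4 in Protocol Section 5.4.1 lowers valganciclovir as creatinine clearance falls: 900 mg once daily at 60 mL/min or more, 450 mg once daily at 40–59, "450 mg every 2 days" at 25–39 and "450 mg twice weekly" at 10–24. In the last row, below 10 mL/min on hemodialysis, valganciclovir is not recommended and the reader is sent to the Medical Monitor.

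The note under the table explains that tablets cannot be used in this row because "the daily dose of valganciclovir tablets required for these patients is less than 450 mg". It then says that "the Investigator will have the option of administering ganciclovir IV at 5 mg/kg QD, after discussion with the Study Medical Monitor".

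Section 5.2.2 has a separate IV provision for patients who cannot tolerate oral dosing: "the Investigator will have the option of administering ganciclovir intravenously (IV) at 5 mg/kg QD". A reduction rule comes next: "In patients who are receiving a dose of valganciclovir less than 900 mg orally once daily, the dose of ganciclovir will be reduced accordingly". The scale is set at 5 mg/kg for each 900 mg.

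Section 1.2.2 says that elimination is mainly renal, recommends lower doses in renal impairment, and names cytopenias and acute renal failure as notable adverse events. SAP Section 3.3.1 repeats the dosing table without the note, so it prints no IV dose for this row.

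**The concern.** Every step down Table 4 lowers the dose. The note then gives, for the worst renal function, the IV dose that Section 5.2.2 treats as the counterpart of full-dose valganciclovir, and it does so straight after saying that these patients need less than half of 900 mg a day. An investigator and a Medical Monitor discussing such a patient would find one IV figure in the dialysis instruction, and it carries no renal reduction.

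What is at stake is the safety of a few patients. The drug is cleared mainly by the kidney, and Section 1.3.2 says that the two study drugs share thrombocytopenia and renal dysfunction as toxicities. Objective response rate, the time-to-event endpoints, sample size and error rates are not involved.

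**Working it through.** **Inputs**

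- Exchange rate (Section 5.2.2): 900 mg valganciclovir to 5 mg/kg ganciclovir, with proportional reduction for patients receiving less than 900 mg once daily.
- Oral doses by creatinine clearance (Table 4): 900 mg once daily at 60 mL/min or more; 450 mg once daily at 40–59.
- Oral requirement below 10 mL/min (note to Table 4): less than 450 mg a day.
- IV dose below 10 mL/min (same note): 5 mg/kg QD.

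**Formula.** IV dose in mg/kg QD = oral once-daily dose in mg × 5/900.

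**The protocol's own figure.** 900 × 5/900 = 5.0 mg/kg QD. This reproduces the dose in Section 5.2.2 and ties it to a clearance of 60 mL/min or more.

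**The reduced case that Section 5.2.2 covers directly.** 450 × 5/900 = 2.5 mg/kg QD, for a patient on 450 mg once daily who cannot take tablets.

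**Side by side**

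| Creatinine clearance (mL/min) | Oral dose | IV dose from the protocol |
|---|---|---|
| 60 or more | 900 mg once daily | 5 mg/kg QD (Section 5.2.2) |
| 40–59 | 450 mg once daily | 2.5 mg/kg QD (Section 5.2.2 ratio) |
| Below 10, on hemodialysis | tablets not usable; requirement below 450 mg a day | 5 mg/kg QD (note to Table 4) |

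The ratio returns 5 mg/kg only for 900 mg. The printed IV dose therefore falls from 5 to 2.5 mg/kg QD as renal function worsens and is back at 5 mg/kg QD in the dialysis row. No other passage prints a reduced IV dose for that row.

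**How often the row might be reached.** Section 1.2.4 reports increased creatinine in 17 of 64 patients in the prior study (17/64 = 26.6%), all Grade 1 or 2. With 0 of 64 at Grade 3 or higher, the one-sided 95% upper bound is 1 − 0.05^(1/64) = 4.6%. That bound concerns Grade 3 or higher creatinine increase, pooled over several dose schedules. It is not a dialysis rate, which would be expected to be lower.

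**The case against.** The case for leaving the text alone is mainly that the situation is rare and supervised:

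- Entry requires a clearance of at least 50 mL/min (inclusion criterion 16), and chemistry is checked weekly in Cycle 1 and every two weeks after that.
- The row advises against valganciclovir. The IV route is an option, and it needs discussion with the Medical Monitor.
- Section 1.3.2 says that valganciclovir adjustments, for example for raised creatinine, follow the prescribing information.
- Table 3 withholds both drugs for study-drug-related Grade 3 non-hematologic toxicity or clinically significant laboratory abnormality, and discontinues them at Grade 4. A fall from 50 to below 10 mL/min would plausibly qualify, although the documents do not reproduce the CTCAE grades. The IV option would then matter mostly for renal failure judged unrelated to study drug.
- The text after Table 3 requires Medical Monitor approval for any re-escalation. Moving from 450 mg twice weekly to 5 mg/kg QD arguably falls under that.

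All of this stands, and it keeps the priority low. None of it corrects the number. The Section 1.3.2 sentence concerns valganciclovir and does not name IV ganciclovir. References 9 and 10 are valganciclovir labels. The monitor's discussion would start from an unreduced figure.

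A further objection is that the Section 5.2.2 reduction applies to patients who cannot tolerate tablets and are receiving less than 900 mg, whereas a patient in the dialysis row receives none. That is correct. A reader might infer that the note breaks the Section 5.2.2 rule, but the documents do not go that far. They show that a patient who has stepped down through Table 4 is pointed to a reduced IV dose by one section and to an unreduced one by the other.

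**Conclusion.** The inconsistency is real and can be seen without any outside source. The note states a requirement below 450 mg a day and prints the IV dose that the protocol elsewhere pairs with 900 mg. At 450 mg once daily the protocol's own rule gives 2.5 mg/kg QD, and the dialysis row gives 5 mg/kg QD. This also runs against the recommendation in Section 1.2.2 to reduce in renal impairment.

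A reader might go further, carry the 5.2.2 ratio into the dialysis row, and conclude that these patients would be overdosed by some multiple. The documents do not support that. The ratio is not written for this row, a requirement of less than 450 mg is not a defined dose, and nothing is said about how much drug dialysis removes. The conclusion is limited to printed doses that do not agree.

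It rests on reading the Section 5.2.2 ratio as the protocol's only oral-to-IV conversion and the Table 4 note as the operative instruction for this row. Few patients should be affected, several controls apply, and no endpoint or analysis changes. It should be fixed, at the low end of that grade.

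**What to change.** In the note to Table 4, delete the figure of 5 mg/kg QD. State instead that any IV ganciclovir given in this row must be renally reduced, with the dose agreed with the Medical Monitor according to the applicable prescribing information. This agrees with Section 1.3.2.

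The documents neither contain nor cite an IV ganciclovir label, so the sponsor should first confirm that a suitable labelled dose for hemodialysis exists and, if it does, add the source to the references. If none is identified, remove the IV option below 10 mL/min and hold both drugs under Section 5.4. Do not print a dose or ceiling derived from the 5.2.2 ratio, because the documents do not define one for this row.

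The cost is one sentence in a protocol amendment, possibly one added reference, and a notice to sites. Removing the option costs slightly more for the few patients concerned, because Section 5.4 holds the two agents in parallel and nanatinostat would stop as well. The SAP needs no change.

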#### 5.4.2. Missed or Vomited Doses

If a scheduled dose of nanatinostat or valganciclovir is missed, the patient should take the missed dose(s) as soon as possible during the same day, but within 8 hours of the missed dose. If more than 8 hours or an entire day has passed, the normal dosing schedule will be resumed the following day without a change in the daily dose or schedule.

If a scheduled dose of nanatinostat or valganciclovir is vomited, the patient should contact the site for consideration of anti-nausea medication and dosing should resume with the next scheduled dose. No replacement dose should be given. If the situation persists, the site should consult the Medical Monitor.

#### 5.5. Prior and Concomitant Medications

Prior and concomitant medications include all vitamins, vaccinations, herbal remedies and overthe-counter and prescription medications.

No other anticancer therapies (including chemotherapy, radiation, antibody therapy, immunotherapy, or other experimental therapies) of any kind are permitted while the patient is receiving treatment with nanatinostat and valganciclovir. Patients are not allowed to participate concurrently in any other therapeutic study.

#### **5.5.1.** Permitted Concomitant Medications

During the time on study treatment, medications required to treat AEs or manage cancer symptoms, and supportive care agents, such as antiemetics, antidiarrheal agents and pain medications are allowed, except if specifically prohibited (see Section 5.5.4). Patients may continue to use concomitant medications previously prescribed to treat non-cancer-related conditions provided that, in the Investigator's judgment, they will not interfere with the study outcomes.

#### **5.5.1.1.** Hematopoietic Growth Factors

The prophylactic use of hematopoietic growth factors is prohibited unless the patient experiences an AE. Granulocyte colony-stimulating factor (G-CSF) agents may be administered in response to Grade ≥3 neutropenia (Table 3). The American Society of Clinical Oncology (ASCO) clinical practice guidelines should be followed (Smith 2015). Hematopoietic growth factors may not be used to allow for patient eligibility at screening.

## 5.5.2. Concomitant Therapy Requiring Caution and/or Action

#### **5.5.2.1.** Corticosteroids

Patients may receive topical or inhaled corticosteroids while on study, or prednisone ≤10 mg per day (or the equivalent). The use of systemic corticosteroids is discouraged because the potential anti-lymphoma effect may confound the interpretation of study drug-related activity. Patients who develop severe conditions requiring systemic corticosteroid therapy may be treated as such and are not required to discontinue participation in the study.

## 5.5.2.2. Proton-Pump Inhibitors

The effect of gastric pH on nanatinostat absorption is not known. Proton-pump inhibitors and H2 antagonists should be excluded from patient use if possible. If they must be given, then do not administer proton-pump inhibitors, H2 antagonists, or antacids within 2 hours prior or within 4 hours post-nanatinostat administration.

## 5.5.2.3. Concomitant Therapies to be Used with Caution with Nanatinostat

A study with recombinant human cytochrome P450 isoforms (CYP450) suggests that nanatinostat is a direct inhibitor of CYP3A4 isoform. In vitro studies indicated that nanatinostat is not metabolized by or induces the activity of CYP3A4. A potential for drug interactions between nanatinostat and drugs that are substrates of CYP3A4 is low but cannot be ruled out (see Appendix 1 Table 11). Please refer to the IB for a detailed description.

Select antiretroviral therapies (ARTs) (saquinavir, tipranavir, darunavir and idinavir) that are metabolized by CYP3A4 should be administered with caution. Coadministration of these ARTs may result in an increase in their systemic exposures. Caution is recommended during the coadministration of these drugs with nanatinostat (particularly saquinavir and indinavir due to their narrow therapeutic index), as well as other CYP3A substrates relevant to the study population (cyclosporine, sirolimus, tacrolimus).

As combined (estrogen-progesterone containing) oral contraceptives are metabolized by CYP3A4, caution is also recommended during the coadministration of these drugs with nanatinostat. Although the potential for drug interactions and risk of venous thromboembolism is low, the use of an alternative method of contraception is recommended.

Transporter studies indicate nanatinostat is likely a substrate of MDR1 and BCRP transporters, but not an inhibitor of these transporters. Therefore, the use of strong MDR1/P-gp and BCRP inhibitors should be approached with caution (see Appendix 1 Table 12).

## 5.5.3. Concomitant Therapies to be Used with Caution with Valganciclovir

Drug-drug interaction studies with ganciclovir/valganciclovir were conducted in patients with normal renal function. Therefore, with concomitant administration of valganciclovir and other renally excreted drugs, patients with impaired renal function may have increased concentrations of ganciclovir and/or the co-administered drug. Such patients should be closely monitored for toxicity of ganciclovir and the co-administered drug. Established and other potentially significant drug interactions conducted with ganciclovir are listed in Appendix 2.

Patients receiving concomitant immunosuppressive agents such as cyclosporine, mycophenolate mofetil, sirolimus and tacrolimus may be at risk for increased hematologic and/or renal toxicity.

Coadministration of the antiretroviral agent didanosine may result in an increase in its concentration and patients should be monitored closely for toxicity (eg, pancreatitis). In patients who are receiving a concomitant medication considered to pose a risk of significant drug interaction with valganciclovir, additional monitoring should be conducted as outlined in Appendix 2.

## 5.5.4. Prohibited Medications

The following medications/therapies are prohibited during the study

- Other investigational and antineoplastic therapies, including anti-CD20 agents
- Prednisone >10 mg per day (or equivalent)
- Live vaccines
- Medications with a known risk of prolonging the QTc interval/TdP (Class Ia
  [disopyramide, quinidine, procainamide] and Class III [sotalol, dofetilide, ibutilide]
  antiarrhythmic agents) (Drew 2010). If during the course of this study the concomitant
  administration of drugs with a known potential to cause TdP is required and cannot be
  avoided, study drug administration must be interrupted until an assessment of the
  potential safety risk has been performed.

# 5.6. Patient Numbering & Treatment Assignment

### 5.6.1. Patient Numbering

At the time of consent, patients will be assigned a 7-digit identification number consisting of a 4-digit site number (eg, 1001) followed by a 3-digit patient number (eg, 101). Patient numbers will be assigned sequentially at each site starting with 101 (eg, 1001-101, 1001-102, 1001-103, etc.).

# **5.6.2.** Treatment Assignment (Including Randomization)

Patients will be enrolled into each cohort based on their primary lymphoma diagnosis to receive the combination nanatinostat plus valganciclovir with exception of Cohort 3a.

The first 20 patients enrolled with PTCL in Cohort 3 will be randomized 1:1 to either Cohort 3a (nanatinostat monotherapy) or Cohort 3b (nanatinostat plus valganciclovir). Randomization will occur at the time of drug dispensation for Cycle 1 Day 1. Following a disease response

assessment at 6 weeks, patients in Cohort 3a with a CR or PR will continue nanatinostat monotherapy. Those in Cohort 3a with stable disease at 6 weeks or disease progression at any time will be offered the option to cross over to combination therapy for the remainder of the study, provided they qualify per hematology, chemistry, no sign of CNS disease progression, and ECOG parameters (see Section 4.1.1).

#### **5.6.3.** Treatment Blinding

This is an open-label study; therefore, treatment assignments will not be blinded.

# 5.7. Study Drug Preparation and Dispensation

## 5.7.1. Study Drug Packaging and Labelling

The study drugs will be released upon receipt of all requested essential documents based on federal, state, and local regulations. Each bottle of study drug will have either a booklet or panel label describing the contents based on regulatory requirements and a place for the pharmacist to record the patient number. Additional information is described in Section 5.1 (nanatinostat) and Section 5.2 (valganciclovir).

# 5.7.2. Drug Supply and Storage

Drug supply and storage is described in Section 5.1 (nanatinostat) and Section 5.2 (valganciclovir). Additional information is provided in the Pharmacy Manual.

## 5.7.3. Study Drug Compliance and Accountability

## **5.7.3.1.** Study Drug Compliance

Patient compliance with study drugs will be assessed by the Investigator and/or study personnel at each patient visit, and information provided by the patient and/or caregiver will be captured in the eCRF. This information must be captured in the source document at each patient visit. Paper diaries will be utilized to record doses and collect tablet counts.

#### 5.7.3.2. Study Drug Accountability

The Investigator or their representative will account for all study drugs supplied by the Sponsor. The Investigator shall maintain adequate records of the disposition of study drug, including dates, quantity, lot numbers, and use by patients. Drug accountability will be reviewed during monitoring visits and at the completion of the study.

# 5.7.4. Study Drug Handling and Disposal

Upon completion of the study, all remaining study drugs at the sites will be accounted for and returned to the Sponsor, or their designee, via a traceable method (UPS, FedEx, etc.) or disposed following institution's Standard Operating Procedures (SOPs), if instructed by the Sponsor.

### 6. SCHEDULE OF EVENTS

The Schedule of Events provided in Section 6.1 lists all the on-study assessments and the visit dates when they are to be performed. Every effort should be made to follow the schedule outlined in the Schedule of Events. Allowed visit windows are specified as follows:

- a. Screening assessments per the Schedule of Events must occur within 28 days (14 days for laboratory assessments, urinalysis, and pregnancy test) of Cycle 1 Day 1.
- b. Vital signs, ECOG performance status, and physical exam should be performed within 28 days of start of study drug (Cycle 1 Day 1). Required laboratory assessments should be performed within 14 days of the start of study drug (Cycle 1 Day 1).
- c. Radiologic assessments must be performed as indicated in Section 6.1. A visit window of ±7 days is allowed. Radiological assessments should stay on schedule even if there are dose holds.
- d. For all other visits, a general  $\pm 3$ -day window is permitted on assessments; the disease assessments window is  $\pm 7$  days.

# **6.1.** Schedule of Events Tables

**Table 5:** Visit/Evaluation Schedule

	Screening a		Cycle 1 (±3 days)				Cycle 2 (±3 days)		Cycles 3+ (±3 days)		ЕОТ	Safety Follow-up b (±3 days)	Long-Term Follow-up (±7 days)	
Day(s) of Cycle c	-28 to -1	-14 to -1	1	8	15	22	4	15	1 (or 4 in Cycle 6)	15	+14 Days After Last Dose	+28 Days After Last Dose	Without PD (q12 weeks)	
Obtain informed consent	X													
Enrollment/Randomization			X											
Patient history														
Complete medical history	X													
Demography	X													
Prior antineoplastic therapies	X													
Inclusion/exclusion criteria	X													
Prior and concomitant medications	X		X				X		X		X	X		
FFPE tumor specimend	X													
Physical examination	X		X				X		X		X			
Weight	X		X				X		X		X			
Height	X		Xw				Xw		Xw					
ECOG performance status	X		X				X		X		X			
Vital signs e	X		X				X		X		X			
Laboratory assessments	-			•	•	•	•	•	•			•		
Hematology f		X	X	X	X	X	X	X	X	X	X			
Chemistry g		X	X	X	X	X	X	X	X	X	X			
Creatinine clearance (Cockcroft-Gault estimation) h		X												

	Scree	eninga	Cycle 1 (±3 days)		/s)	Cycle (±3 day		Cycles 3+ (±3 days)		ЕОТ	Safety Follow-up b (±3 days)	Follo	-Term ow-up days)	
Day(s) of Cycle c	-28 to -1	-14 to -1	1	8	15	22	4	15	1 (or 4 in Cycle 6)	15	+14 Days After Last Dose	+28 Days After Last Dose	Without PD (q12 weeks)	With PD (q6 months)
Serum immunoglobulins i			X						X		X			
Coagulation f		X									X			
Urinalysis		X												
Hepatitis serology j	X													
Serum pregnancy test k		X												
Serum or urine pregnancy test k			X				X		X		X	X	Xq12wks for 6 mos	Xq12wks for 6 mos
Disease assessments				l							I		,	
CT with contrast (or MRI) of brain	X													
 FDG-PET/CT 	X								X Wks 8, 16					
CT with contrast (or MRI) of neck, chest, abdomen, and pelvis m	X								X Wks 8, 16, 24 + q12wks		X		X q12wks	
Bone marrow biopsy n	X													
Safety assessments				•		•	•							
12-lead ECG°	X		[X]								X			
Adverse events	X		X	X	X	X	X	X	X	X	X	X		
CMV, HHV-6, HHV-8, HIV levels p			X		X		X		X		X	X		
EBV DNA levels p	X		X		X		X		X		X	X	X	
Pharmacokinetics														
PK sampling (Stage 1) q							[X] q		[X] q					

	Screeninga		Cycle 1 (±3 days)					Cycle 2 (±3 days)		es 3+ lays)	ЕОТ	Safety Follow-up b (±3 days)	Follo	Term w-up lays)
Day(s) of Cycle c	-28 to -1	-14 to -1	1	8	15	22	4	15	1 (or 4 in Cycle 6)	15	+14 Days After Last Dose	+28 Days After Last Dose	Without PD (q12 weeks)	With PD (q6 months)
PK sampling (Stage 2) q							Xq							
Biomarkers r														
Immunophenotype and function, and mutation analysis s			X						X		X			
Histone acetylation t			X											
On-study biopsy/fine needle aspirate (optional with disease progression or relapse) u							X		•					
Nanatinostat/valganciclovir dispensing/return			X				X		X		X			
Anti-lymphoma therapies since discontinuation of study treatment and response											X	X	X	X
Survival assessment v													X	X

Abbreviations: CT = computed tomography; CMV = cytomegalovirus; DNA = deoxyribonucleic acid; EBV = Epstein-Barr virus; ECG = electrocardiogram; ECOG = Eastern Cooperative Oncology Group; EOT = End of Treatment; FFPE = formalin-fixed paraffin-embedded; HHV = human herpesvirus; HIV = human immunodeficiency virus; mo = month; MRI = magnetic resonance imaging; PD = progressive disease; FDG-PET = fluorodeoxyglucose positron emission tomography; PK = pharmacokinetic; q = once; wk = week.

Note: Brackets ("[X]") indicate procedures performed in Stage 1 only.

- a. **Screening** The Screening visit may be conducted over multiple days in the 28 days prior to Cycle 1 Day 1 or conducted as a single visit within 14 days of Cycle 1 Day 1.
- b. Safety Follow-up Visit must be conducted in-person.
- c. **Visit windows** There is a ±3-day window allowable for each clinic visit. The End of Treatment visit must be completed within 14 days after the last dose. The Safety Follow-up visit has a +3-day allowable window, and Long-term Follow-up has a ±7-day allowable window. For disease assessments, a ±7-day window is allowable (not applicable during Screening).
- d. **Formalin-Fixed Paraffin-Embedded (FFPE) tumor specimen** Eligibility will be based on local pathology review; confirmation of diagnosis by central pathology laboratory is not required for entry or initiation of treatment. A FFPE tumor block and/or 15 unstained slides of a representative tumor specimen

or lymph node must be confirmed to be available at the time of screening and must be submitted to the central pathology laboratory within 8 weeks after Cycle 1 Day 1.

A recent biopsy is ideal, but if not available, an archival biopsy may be submitted, provided the tumor specimen meets the criteria described in Section 7.1.5. The specimen must be representative of the current disease (eg, for patients who have relapsed, the biopsy specimen should have been taken after the most recent relapse). Details will be discussed in the separate Pathology Manual. De-identified pathology reports associated with these tissues are also required and must be sent to the central pathology laboratory with the tissue and/or slides.

- e. **Vital signs** Vital signs include heart rate, blood pressure, and temperature. For patients requiring serial PK draws and ECGs, vital signs should be collected following ECGs and prior to the PK blood draw at pre-dose and 1, 2, and 4 hours post-dose on Cycle 2 Day4 (ECG and vital signs are not performed at the 6-hour post-dose PK draw). At time points requiring ECGs, vital signs, and PK blood draws, assessments should be performed in as short of a timeframe as possible and in this order: ECG, vital signs, then blood draw.
- f. **Hematology and coagulation** Hematology includes complete blood count to include white blood cells (WBCs) with differential, red blood cells (RBCs), hemoglobin (Hgb), hematocrit, platelets, mean corpuscular volume (MCV), and mean corpuscular hemoglobin (MCH). Coagulation includes prothrombin time (PT) or International Normalized Ratio (INR) and activated partial thromboplastin time (aPTT).
- g. **Chemistry** Chemistry includes sodium, potassium, chloride, bicarbonate, blood urea nitrogen, creatinine, glucose, calcium, phosphate, magnesium, aspartate aminotransferase (AST), alanine aminotransferase (ALT), total bilirubin, alkaline phosphatase, total protein, albumin, uric acid, lactate dehydrogenase (LDH), and serum amylase.
- h. Creatinine clearance (Cockcroft-Gault estimation) The Cockcroft-Gault formula will be used to calculate estimated creatinine clearance (CrCl):
  - Males: CrCl (mL/min) = (140 age) × (weight [kg]) / 72 × (serum creatinine [mg/dL]); for females, the formula is multiplied by 0.85.
  - By SI units, CrCl (mL/min) = (140 age) × (weight [kg]) × 1.23 / (serum creatinine [μmol/L]); for females, the formula is multiplied by 0.85.

Valganciclovir dose will be adjusted based on CrCl as described in Section 5.4.1 for patients who develop creatinine elevations/impaired renal function while on study.

- i. **Serum immunoglobulins** Samples will be collected to evaluate serum immunoglobulins including quantitative levels of IgA, IgE, IgG and IgM. Samples will be collected pre-dose and every 3 cycles starting at Cycle 3 Day 1 (Day 1 of Cycles 3, 6, 9, 12, etc.) and at the EOT visit.
- j. **Hepatitis screening** Hepatitis B virus (HBV) surface antigen (Ag), HBV core and surface antibody (Ab), HBV DNA polymerase chain reaction (PCR; only for patients with positive HBV core Ab or surface Ag), hepatitis C virus (HCV) Ab (any patient positive for HCV Ab will be evaluated by qPCR).
- k. **Pregnancy testing** Pregnancy testing is only required for females of childbearing potential. Serum test must be performed during screening. Serum or urine tests are to be performed at the beginning of each cycle, the EOT visit, the 28-day Safety Follow-up visit, and every 12 weeks for 6 months following the last dose of study drug.
- 1. FDG-PET/CT Scans will be performed at Screening, Week 8, Week 16 (±7 days), and subsequently for evaluation of a possible CR or PR. *Diagnostic* contrast-enhanced CT scans obtained as part of a PET/CT scan may be used in lieu of dedicated CT scans.
- m. CT with contrast (or MRI) of neck, chest, abdomen, and pelvis A diagnostic contrast-enhanced CT (or MRI, if CT contraindicated) will be conducted at Screening, Week 8, and Week 16, Week 24 then every 12 weeks until relapse or disease progression (Week 36, 48, 60, etc.), ±7 days. MRI may be performed only if CT with contrast is contraindicated in the opinion of the Investigator or if frequent CT scans are not allowed according to local IRB/IEC. The same imaging modality used at screening must be used for all response evaluations throughout the study to ensure consistency across the different time points for each patient. A scan to confirm an unconfirmed PR or unconfirmed CR ≥4 weeks later may also be performed.

For patients who discontinue due to relapse/progression, the EOT visit FDG-PET/CT and/or CT with contrast is not needed if the last scan was within 4 weeks of the EOT visit.

- n. **Bone marrow biopsy** A recent bone marrow biopsy, conducted within 12 weeks of Cycle 1 Day 1, is acceptable as the screening biopsy (if the biopsy is available for review by central pathology). If no such recent bone marrow biopsy is available, then re-biopsy will be required prior to enrollment except as noted in Section 7.1.7.2. During the study, a repeat bone marrow biopsy is required only for patients who have attained a complete response (CR) and had bone marrow involvement at screening. The bone marrow biopsy should be performed within 28 days after the criteria for radiological CR have been met. For patients with Hodgkin lymphoma and DLBCL, a baseline bone marrow biopsy is not necessary if the PET/CT demonstrates bone disease.
- o. 12-Lead ECG All ECGs will be performed in triplicate. Average corrected QT interval using Fridericia's method (QTcF) is to be calculated to confirm eligibility. For patients enrolled in Stage 1, ECGs will be performed in triplicate as follows: 2 ECGs will be performed pre-dose within 1 hour of dosing at least 15 minutes apart. Post-dose ECGs will be performed prior to and as close as possible to PK blood draws at 1, 2, and 4 hours post-dose on Cycle 2 Day 4. An additional triplicate ECG will be obtained at screening, Day 46 (Cohort 3a only) visit, and EOT. Detailed instructions on ECGs are provided in Section 7.3.2.8 and in the separate ECG Manual.
- p. **EBV, CMV, HHV-6, HHV-8, HIV levels** Plasma samples will be collected to investigate circulating EBV, HHV-8, HHV-6, CMV, and HIV (HIV+ patients only). EBV levels will be utilized for both safety and biomarker analyses, and will continue every 12 weeks during Long-term Follow-up until disease progression or the start of new lymphoma treatment. Only EBV levels will be measured at Screening.
- q. **PK sample collection** During Stage 1 of the study PK will be collected on Cycle 2 Day 4 and Cycle 6 Day 4 from Cohorts 1, 2, 3b, 4, 5, 6, and 7 at predose and 1, 2, 4, and 6 hours post-dose (±15 minutes). For patients in Cohort 3a, PK will be conducted at Cycle 2 Day 4 of the monotherapy and repeated on Cycle 2 Day 4 and Cycle 6 Day 4 of the combination therapy for patients that cross over. At time points requiring ECG, vital signs, and PK blood draw, assessments should be performed in as short of timeframe as possible and in this order: ECG, vital signs, then blood draw. During Stage 2 of the study sparse PK sampling will be conducted at selected sites. Sparse sampling will occur at Cycle 2 Day 4. Patients will be assigned one of 3 sampling schedules:
  - Pre-dose and 4 hours post-dose (±15 minutes)
  - 0.5 and 2 hours post-dose (±15 minutes)
  - 1 and 6 hours post-dose (±15 minutes)
- r. Exploratory biomarkers Blood draws for exploratory biomarkers should be taken prior to the patient taking study medication on that day.
- s. Immunophenotype and immune function, and mutation analysis Peripheral blood mononuclear cells (PBMCs) and plasma will be collected pre-dose and every 3 cycles starting at Cycle 3 Day 1 (Day 1 of Cycles 3, 6, 9, 12, etc.) and at the EOT visit. Cycle 1 Day 1 pre-dose sample may be collected during screening within 14 days of Cycle 1 Day 1.
- t. **Histone acetylation** PBMCs for histone acetylation will be collect pre-dose and at 3 hours (±15 minutes) post-dose on Cycle 1 Day 1.
- u. **On-study biopsy** FFPE tumor specimens collected during the study as standard of care should be provided to the central pathology laboratory, along with a frozen tissue specimen, if available. For patients with disease progression on study, a frozen and an FFPE tumor specimen will be provided to the central pathology laboratory.
- v. **Subsequent anti-lymphoma therapies and response** Patients will be contacted by telephone or e-mail for assessment of additional therapy, response status, and survival following the Safety Follow-up assessment.
- w. **Height** Height measurements should be obtained for all patients at Screening. Post-baseline height measurements should be obtained for patients 12 to 17 years of age.

Table 6: Visit/Evaluation Schedule for Cohort 3a (Nanatinostat Monotherapy), Days 1-43

	Nanatinostat Monotherapy Cycle							
Day(s) of Cycle c	1	15	29	431,2,3				
Enrollment/Randomization	X							
Prior and concomitant medications	X	X	X	X				
Physical examination	X		X					
Weight	X		X					
ECOG performance status	X		X	X				
Vital signs e	X		X	X				
Laboratory assessments								
Hematology f	X	X	X	X				
Chemistry g	X	X	X	X				
Creatinine clearance (Cockcroft-Gault estimation) h				X				
Serum immunoglobulins i	X			X				
Coagulation f				X				
Urinalysis				X				
Serum or urine pregnancy test k	X		X	X				
Disease assessments								
 FDG-PET/CT 				X				
CT with contrast (or MRI) of neck, chest, abdomen, and pelvis 				X				
Safety assessments								
12-lead ECG°	X			X				
Adverse events	X	X	X	X				
CMV, HHV-6, HHV-8, HIV levels p	X	X	X	X				
EBV DNA levels p	X	X	X	X				
Pharmacokinetics								
PK sampling q	X							
Biomarkers r								
Immunophenotype and functions	X							
Histone acetylation t	X							
On-study biopsy/fine needle aspirate (optional with disease progression or relapse) u			X					
Nanatinostat dispensing/return	X		X					

Abbreviations and lettered footnotes are defined in Table 5. Numbered footnotes are defined below.

1. If a patient has stable or progressive disease AND qualifies to continue (safety laboratory assessments, no sign of CNS disease progression, and ECOG status) at the Day 43 visit (or progressive disease prior to Day 43), the patient may switch to the combination therapy. Crossover to combination therapy must occur within 7 days of the disease assessment. The Day 43 visit (considered the end of monotherapy visit for these patients) and the Cycle 1 Day 1 visit for combination therapy may be combined into a single visit. Patients must complete the

- Day 43 Monotherapy Disease Assessment and qualify prior to beginning the Cycle 1 Day 1 of the nanatinostat/valganciclovir combination therapy.
- 2. If a patient discontinues monotherapy prior to the Day 43 disease assessment for reasons other than disease progression the patient will follow the EOT, Safety Follow-up, and Long-term Follow-up procedures outlined in Table 5.
- 3. If patient has a response (complete or partial response) to nanatinostat monotherapy at the Day 43 disease response assessment, the patient will continue monotherapy treatment, restarting assessments at Day 57 (Cycle 3, Day 1). Visits will continue every 14 days as described in Table 5.
